1. STUDY OBJECTIVES/HYPOTHESIS

Primary Objective(s)

Primary aim: Compare the diagnostic yield of Magnetic Resonance Enterography (MRE) with Small-Bowel Capsule Endoscopy (SBCE) in pediatric patients with known

Inflammatory Bowel Disease (IBD) including Crohn's disease (CD) or indeterminate colitis (IC).

Secondary Objective(s)

1. To determine the detection rate of small bowel disease / complications, subjected to a strategy of Wireless Capsule Endoscopy (WCE) – small bowel screening / surveillance vs MRE in a pediatric tertiary medical institution.
2. Compare sensitivity and specificity of both MRE and WCE in identifying patients with active vs. inactive CD and IC as defined by the Pediatric Crohn's disease activity index.
3. To correlate the findings detected on WCE by Lewis score with Crohn's disease activity index.

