Overall tolerance and safety: WCE is safe in children approximately 9 years of age and older, endoscopic placement is feasible in individuals refusing or unable to swallow the capsule but adds to the potential morbidity and expense of the procedure. WCE has been safely performed in children as small as 11.5 kg [4]. Jensen and colleagues studied the factors associated with incomplete WCE studies and their diagnostic yield in pediatric patients. In this study, 22% of the WCE studies were incomplete, and in 12 (44%) of these were normal pre-WCE radiologic findings [4].

WCE should be used with caution and most likely contraindicated in patients with known swallowing disorders, gastrointestinal obstruction and fistulas. The risk for WCE retention (which is defined as capsule remains in digestive tract for a minimum of 2 weeks or it requires direct intervention to aid in its passage) in Crohn's disease patients is estimated to be 5%–13% [12]. Even though Crohn's disease is reported to have the most

common retention rate it is reported in metanalysis that retention rate is 2.6% in all prospective and retrospective studies [13].

Atay and colleagues investigated the risk factors for capsule retention in their cohort (n = 207) of pediatric patients studied by WCE[14]. Capsule retention complicated 1.4% of studies; all in known Crohn's patients. The risk in known CD patients was therefore 5.2%, and rose to 37% if there had been a prior small bowel series showing small bowel disease, and to 43% if the patient's body mass index was less than the 5th percentile, presumably indicative of more severe, longstanding small bowel involvement [14].

The Patency Capsule (Agile ®) was developed, tested, and shown to greatly curtail the possibility of small bowel capsule retention and therefore obviate the need for surgery[15]. A pre-WCE, patency capsule (PC) strategy has completely removed the incidence of capsule retention[15]. The caveat to PC testing is that it also impacts the utility of WCE overall in so far as a proportion of patients cannot thus be studied (failed PC passage). The Patency capsule is identical in shape and size to the actual WCE device but in the presence of small intestinal enzymes it will dissolve starting at 30 hours post ingestion, thus slow passage or retention of PC in the small bowel signals a risk of capsule retention and are usually interpreted as a contraindication for WCE.[16]

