3. STUDY DESIGN

- Prospective single blinded comparison of a cohort of pediatric patients with indeterminate colitis (IC) or Crohn's disease (CD) who are scheduled to undergo

routine small bowel screening or surveillance using MRE. Subjects will swallow a patency capsule (PC) to study bowel patency. If MRE shows stenosis or stricture subject and caregivers will be given the opportunity to continue with the study or withdraw. Those patients, who pass an intact PC, usually within 40 hours, will ingest the wireless capsule endoscopy (WCE). The WCE will be performed within 1 week of completion of MRE. Both modalities diagnostic yields will be compared to detect Crohn's disease lesions/complications and correlate the findings with Pediatric Crohn's Disease Activity Index (CDAI).

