4. TARGET STUDY POPULATION SPECIFICS

Study participants (n=50) ages 4 – 17.99 years of age will be recruited for this study. Patients will be identified for recruitment after an initial evaluation in gastroenterology clinic at Children's Mercy (CM), if they are diagnosed with IBD and planned to have MRE as part of standard of care for clinical indication to evaluate small bowel disease.

Inclusion Criteria:

- Patients aged 4 to 17.99 years at time of investigation
- IBD/CD and IBD/IC diagnosed based on standard clinical – histologic criteria
- Patient is scheduled to have MRE as standard of care for evaluation of disease severity/ complication.
- Signed permission/assent/consent

Exclusion Criteria:

- IBD diagnosis not established
- Recent intestinal tract surgery / resection involving small bowel
- Use of NSAIDs 4 weeks prior to the Capsule endoscopy study.
- Patients are on prokinetic medication.
- Swallowing disorders, esophageal stricture or patients unable to swallow the capsule.
- Presence of gastrointestinal obstruction or ileus.
- Patient with implanted electro-medical device or pacemakers.

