8. STATISTICAL CONSIDERATIONS

Measures

1. Detection rate of upper intestinal lesions in known IBD – CD undergoing WCE vs radiologic modality.
2. Definitive diagnosis of SB involvement of patients undergoing WCE vs radiologic modality in indeterminate IBD.
3. Complication rate for WCE vs 1st radiologic testing
4. Retention rate of WCE
5. The Crohn's disease activity index and its relation with the findings on both modalities
6. Lewis score on WCE

Sample size determination

With a sample size of 34 participants we will have 80% power probability to detect the 23 % difference in IBD small intestinal MRE findings and WCE detection rate similar to previously reported pediatric studies [11]. This determination uses a Chi-Square test and a two-sided significance level of 0.05. Subjects whose MRE results show findings that are contraindicated with WCE will be considered screen failures. We anticipate around 20% screen failure rate and intend to recruit 40 subjects to obtain a sample size of 34 evaluable subjects.

Data Analyses

The disease activity detection rate of MRE and WCE will be compared using McNemar's test and Chi square test. The sensitivity and specificity of both tests will be calculated based on a gold standard of classifying disease activity using Crohn's disease activity index (CDAI). The person correlation coefficient or spearman rank correlation coefficient

will be utilized to assess agreement between lewis capsule endoscopy score and CDAI. All p values will be 2 sided with statistical significance evaluated at 0.5 alpha level.

HUMAN SUBJECTS

Institutional Review Board (IRB) Review and Informed Consent

This protocol, and any subsequent modifications, will be reviewed and approved by the Pediatric IRB at The Children's Mercy Hospital & Clinics.

We request a partial Waiver of HIPAA Authorization for pre-recruitment activities.

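### Screen failure on MRE findings lets one of the two compared tests help decide who is compared, and no planned analysis keeps those subjects for the strategy objective

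*Combined protocol and SAP*

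**What the plan says.** Section 8 (Sample size determination) sets the rule: "Subjects whose MRE results show findings that are contraindicated with WCE will be considered screen failures". It expects roughly 20% screen failures and plans 40 recruited for 34 evaluable. The detection rates are then compared by McNemar's test and a chi-square test. No analysis population is named, and there is no rule for subjects who had an MRE but no WCE.

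The objectives in Section 1 are wider. The primary aim concerns children with known Crohn's disease or indeterminate colitis, and secondary objective 1 reads "To determine the detection rate of small bowel disease / complications, subjected to a strategy of Wireless Capsule Endoscopy (WCE", followed by the comparison with MRE. Neither is restricted to children able to have a capsule.

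Other sections bear on who reaches WCE:
- Section 3: "If MRE shows stenosis or stricture subject and caregivers will be given the opportunity to continue with the study or withdraw". Section 5 (Post Patency Capsule Swallow) likewise leaves the decision to the family once the MRE and patency results have been discussed.
- Section 3 adds a second gate: "Those patients, who pass an intact PC, usually within 40 hours, will ingest the wireless capsule endoscopy (WCE".
- Section 4 lists as an exclusion "Presence of gastrointestinal obstruction or ileus", but not fistula or small-bowel stricture.
- Section 2 says "WCE should be used with caution and most likely contraindicated in patients with known swallowing disorders, gastrointestinal obstruction and fistulas", and concedes that with patency testing "a proportion of patients cannot thus be studied (failed PC passage".

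Section 6 has one radiologist re-read the MRE of all subjects. It does not say whether screen failures are included.

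**The concern.** In a paired comparison of two tests, neither test's result should decide who is compared unless the target population is defined that way. Here a finding on MRE can remove a child before WCE. Such a child probably counts as an MRE detection, since Section 3 says "Both modalities diagnostic yields will be compared to detect Crohn's disease lesions/complications" and the removing findings are likely to be complications of that kind. Dropping these children takes detections from MRE and none from WCE's observed results.

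Two questions are affected differently. One is the paired yield in children who have both tests. The other is what a WCE strategy detects, compared with MRE, in the children to whom it would be offered. For the second, children who cannot reach WCE are part of the answer. Reported alone, the completer result could be read as the strategy result.

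**Working it through.** **Inputs.** From Section 8: planned difference 23 points, 34 evaluable, 40 recruited, expected screen failure about 20%. Assumed, because the documents do not say: how many of the lost are MRE-positive (*m*), and what WCE would have shown in them.

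**The plan's own figures.** 40 − 34 = 6 lost, and 6/40 = 15%, not 20%. A 20% loss from 40 leaves 32. I use the plan's counts, 6 lost of 40. The evaluable number of 34 cannot be reproduced, because neither the two detection rates nor the discordant share is given. Nothing below depends on 34 being the right size.

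**Step 1: net count.** A 23-point difference in 34 subjects is 0.23 × 34 = 7.82 net patients in favour of WCE.

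**Step 2: put the 6 lost back.** With *m* of them MRE-positive, the difference over all 40 is
- (7.82 − *m*)/40 if WCE not done is scored as no yield;
- (7.82 + 6 − *m*)/40 if it is scored as positive.

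| MRE-positive among the 6 lost | WCE not done = no yield | WCE not done = positive |
|---|---|---|
| 0 | 7.82/40 = +19.6 points | 13.82/40 = +34.6 points |
| 3 | 4.82/40 = +12.1 points | 10.82/40 = +27.1 points |
| 6 | 1.82/40 = +4.6 points | 7.82/40 = +19.6 points |

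The two scorings always differ by 6/40 = 15 points.

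**Step 3: strategy question.** If a WCE that is not done yields nothing, only the no-yield column applies. Every entry in it is below 23, even with no MRE-positive subject among the lost.

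**Step 4: paired-yield question.** Here the WCE result in the lost is simply unknown.
- All 6 MRE-positive, with WCE positive in a share *w*: the difference is (7.82 − 6(1 − *w*))/40. This runs from +4.6 (*w* = 0) to +19.6 (*w* = 1), always below 23. The reason is general: an MRE-positive subject adds 0 or −1 to the net count, so restoring such subjects lowers any positive difference.
- Three MRE-positive and three unrestricted on both tests: from (7.82 − 6)/40 = +4.6 to (7.82 + 3)/40 = +27.1. This range contains 23, so the direction is not fixed.

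**Step 5: which findings remove a subject.** Section 8 lists none. Section 2 mentions obstruction and fistulas, Section 4 excludes obstruction and ileus, and Sections 3 and 5 let families continue after stenosis or stricture. The number lost because of the MRE result depends on how these are reconciled. If subjects with stricture may continue, fewer are lost.

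**The case against.** The strongest reply is that a comparison in completers is what the design intends. The Measures in Section 8 refer to patients who undergo WCE, Section 4 already excludes several groups who cannot have a capsule, and McNemar's test needs both results. This stands for the paired analysis, which is legitimate in that subgroup. It does not cover secondary objective 1, and the restriction is nowhere stated as the target population.

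Second, the word strategy is not defined, and scoring WCE not done as no yield is only one reading. Section 2 treats prior imaging or a patency capsule as standard before WCE, so a WCE strategy might include the gate. This also stands, and is why both scorings are needed.

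Third, Sections 3 and 8 can partly be read together: stricture leads to family choice, while a finding that meets a Section 4 exclusion leads to screen failure. The Section 2 sentence is background, not an eligibility rule. That narrows the conflict but does not settle it, because Section 8 does not say which findings it means.

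Fourth, the absence of an all-subjects analysis is inferred from silence. Nothing forbids one, but none is planned.

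A reader might infer two stronger conclusions that the documents do not support:
- **That the WCE advantage is bound to be inflated.** Positivity on MRE is not defined, and for subjects lost through patency failure or withdrawal without a removing finding the direction is unknown.
- **That MRE would overtake WCE.** With 8 of 40 lost, (0.23 × 32 − 8)/40 = (7.36 − 8)/40 = −1.6 points. This needs the full 20% loss, every lost subject MRE-positive, and every one scored WCE-negative. Section 8 does not say that the 20% are all removed for MRE findings, and its own counts imply 15%.

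**Conclusion.** The point holds and should be fixed, with medium confidence. By a stated rule, one of the compared tests helps select who is compared, and the plan has no analysis that addresses the strategy objective in the subjects that rule removes. The paired test is not invalid; its scope is unstated.

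The +4.6 to +19.6 range is a bound, not an estimate of bias. It assumes a 23-point difference in 34 completers, 6 lost of 40, and all 6 positive on MRE. The actual size cannot be derived from the documents, because it depends on the definition of a positive MRE, on the reasons for loss, and on which findings trigger removal.

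**What to change.** 1. Keep the McNemar analysis and state that it applies to subjects eligible for and completing WCE.
2. Define a positive MRE. State that the single-radiologist re-read includes screen failures, and report MRE yield in all consented subjects with an MRE.
3. Tabulate WCE not done by reason (MRE finding, patency failure, withdrawal), with the MRE result. Record this on the data collection form, because Section 6 has the pre-recruitment log destroyed when enrolment is completed.
4. For secondary objective 1, add a sensitivity analysis over all consented subjects, with WCE not done scored once as no yield and once as positive.
5. Reconcile Sections 3, 5 and 8 on which MRE findings make a subject a screen failure and how subjects with stenosis or stricture are handled. The mentions in Sections 2 and 4 should be made consistent with the result. Which clinical rule applies is for the investigators to decide.

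The cost is wording, one table and one sensitivity analysis. No new procedure is needed: the MRE is standard of care and Section 5 allows consent before or at that visit. The re-read grows slightly if screen failures were not already meant to be in it. The downside is that the bounds are about 15 points wide at 6 of 40 lost, and the WCE advantage may look smaller.

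### Forty recruits at the plan's own 20% screen-failure rate are expected to give 32 evaluable pairs, not 34, and the 20% makes no allowance for failed patency capsules

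*Combined protocol and SAP*

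**What the plan says.** Section 8 (Sample size determination) sizes the study as follows: "With a sample size of 34 participants we will have 80% power probability to detect the 23 % difference", and "This determination uses a Chi-Square test and a two-sided significance level of 0.05". It names one source of loss: "Subjects whose MRE results show findings that are contraindicated with WCE will be considered screen failures". It then sets the recruitment target: "We anticipate around 20% screen failure rate and intend to recruit 40 subjects to obtain a sample size of 34 evaluable subjects".

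Section 4 gives another target: "Study participants (n=50".

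Between MRE and a complete pair there is a further step. Section 3 states: "Those patients, who pass an intact PC, usually within 40 hours, will ingest the wireless capsule endoscopy (WCE". Section 5 repeats that condition. Section 2 acknowledges the consequence, namely that "a proportion of patients cannot thus be studied (failed PC passage", but gives no rate. Section 2 also reports that in a cited pediatric series "22% of the WCE studies were incomplete".

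On reading the capsule, Section 6 calls a study positive when clear mucosal abnormalities are observed. It does not require the study to be complete. No section says whether an incomplete study without a lesion is evaluable.

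Sections 3 and 5 let families choose whether to continue after MRE shows a stricture or a raised retention risk. Section 8 treats contraindicating MRE findings as screen failure.

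**The concern.** The primary aim compares two tests in the same children, so the number of children with both results determines the power. If the recruitment target does not deliver the stated number of pairs, the 80% power claim does not describe the study that will be run. There are two separate defects. The stated loss rate and the stated target do not give the stated evaluable number. In addition, the loss rate is defined so that it leaves out a loss the protocol builds into its own procedures.

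**Working it through.** **Inputs.** From Section 8: 34 evaluable, 40 recruits, about 20% screen failure, a 23-point difference, two-sided 0.05. From Section 4: 50 participants. From Section 2: 22% incomplete WCE studies in the cited series, and no patency-capsule failure rate. Assumed: patency-capsule failure of 0 to 20% among those remaining after MRE, with the losses independent.

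**1. The plan's own figure.** Recruits needed = evaluable / (1 - loss).
- At 20% loss: 34 / 0.80 = 42.5, so 43.
- Evaluable from 40: 40 x 0.80 = 32.
- Loss that 40 recruits can absorb: 1 - 34/40 = 15%.
- The stated 40 is close to 34 x 1.2 = 40.8, which multiplies by 1 plus the loss where it should divide by 1 minus the loss. It is also exactly 34 / 0.85.

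The gap of two exists before any omitted loss. It remains if the 20% is read as covering all causes. Taking the number evaluable as binomial with n = 40 and probability 0.80, the chance of reaching at least 34 is 29%.

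**2. Adding patency-capsule failure.** Expected pairs = recruits x (1 - 0.20) x (1 - capsule failure).

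| Capsule failure (assumed) | From 40 | From 50 | Recruits for 34 pairs |
|---|---|---|---|
| 0% | 32.0 | 40.0 | 34/0.80, so 43 |
| 10% | 28.8 | 36.0 | 34/0.72, so 48 |
| 20% | 25.6 | 32.0 | 34/0.64, so 54 |

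At 10% capsule failure, the chance that 40 recruits give at least 34 pairs is 4%. Fifty recruits cover a further loss of up to 15% (50 x 0.80 x 0.85 = 34).

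**3. Power.** Both tests are done in each child, so I used exact McNemar power at two-sided 0.05. The plan does not state the discordant proportion, so it is an assumption. The smallest value compatible with a 23-point difference is 23%, with every discordant pair in the same direction. The exact test then rejects with 6 or more discordant pairs (2 x 0.5^6 = 0.031; with 5 it is 0.0625), so power is the probability that a binomial(n, 0.23) count is at least 6. For 33% discordance the split is 28% against 5%.

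| Pairs | 23% discordance | 33% discordance |
|---|---|---|
| 34 | 83% | 58% |
| 32 | 78% | 54% |
| 28 | 65% | 46% |
| 25 | 53% | 40% |

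The 29 pairs expected at 10% capsule failure lie between the rows for 32 and 28. The 26 expected at 20% lie between the rows for 28 and 25. The plan's 34 cannot itself be re-derived, because Section 8 gives neither the two detection rates nor the discordance.

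**4. Incomplete WCE, as a bound only.** If every incomplete study were discarded and no patency capsule failed: 40 x 0.80 x 0.78 = 24.96, about 25 pairs. If half were kept: 40 x 0.80 x 0.89 = 28.5 from 40 recruits, and 50 x 0.80 x 0.89 = 35.6 from 50.

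**The case against.** A reader might infer that the 22% incomplete studies are lost as well, so that 40 recruits give 25 pairs and 53% power. The documents do not support that. Section 2 reports those studies as incomplete, not as undiagnostic. Section 6 makes an observed abnormality sufficient for a positive reading, so an incomplete study that shows a lesion already counts. Only an incomplete study without a lesion is unaddressed, and nothing in the plan says it is discarded. The 22% is also a literature rate from another series, not a planning assumption for this trial, and the documents do not say whether that series screened with a patency capsule. The 25-pair figure is therefore a bound on one scenario and not the expected number.

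A reader might also infer that the omitted losses cause the shortfall. They widen it, but the two-subject gap comes from the 20% and the 40 alone. Nor is it certain that 40 recruits will fall short; at 20% loss there is a 29% chance that they do not.

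Three further objections have weight. Section 4's 50 would cover MRE loss plus 10% capsule failure, but it conflicts with the 40 in Section 8 and no derivation is given for it. Capsule failure may overlap with strictures seen on MRE, in which case independence overstates the combined loss. MRE losses may be below 20%, because Sections 3 and 5 let families continue after a stricture finding. That last point exposes an inconsistency with Section 8 and does not rescue its figure, which uses 20%.

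**Conclusion.** The concern holds. On the plan's own figures, 40 recruits are expected to give 32 evaluable subjects, not 34; reaching 34 takes 43. This part needs no assumption beyond the plan's 20%. The allowance also omits patency-capsule failure, which the protocol recognises as a reason why patients cannot be studied. With an assumed 10% to 20% failure, the expected number is about 29 to 26 pairs from 40 recruits, or 36 to 32 from 50.

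The cost in power is modest for the arithmetic gap alone (83% to 78% at 23% discordance, 58% to 54% at 33%) and larger once capsule failures are added (65% and 46% at 28 pairs). These figures rest on assumed discordance, an assumed capsule-failure range and independent losses. They do not rest on discarding incomplete capsule studies.

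**What to change.** 1. Reconcile the 40 in Section 8 with the 50 in Section 4, and state one target.
2. Correct the inflation to evaluable / (1 - loss). List MRE contraindication and patency-capsule failure as separate losses, and show an assumed range for the second. Restate expected pairs and McNemar power across that range, with the assumed discordance written down.
3. State that incomplete WCE studies remain in the primary analysis: positive if a lesion is seen, which already follows from Section 6, and not detected if none is seen. Do not also deduct them as lost pairs.
4. Add a sensitivity analysis that excludes incomplete studies without a lesion. Quote 25 pairs from 40 recruits (53% power at 23% discordance, before any capsule failure) only as the bound if all 22% were lost.
5. Reconcile Sections 3, 5 and 8 on whether a stricture seen on MRE is a screen failure.

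The cost is a rewritten sample-size paragraph, one evaluability sentence and one sensitivity analysis. The stated evaluable number and power become less favourable, or the recruitment target rises. Counting lesion-free incomplete studies as not detected may also lower the WCE yield and so narrow the difference under test.

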with a parent/caregiver at school during the lunch period. The patient or caregiver must record the exact time the pill is swallowed to calculate

time till x-ray. This will allow for the subsequent miralax dose and any necessary x-rays to take place after school hours.

- Subjects should not be around electromagnetic fields while PC procedure is performed
- Subject will receive Miralax and instructions for WCE home prep.
- Post Patency Capsule Swallow
 - A follow up phone call will take place with the subject and family the day following patency capsule ingestion. Subjects will return to CM radiology for an abdominal x-ray within 28-40 hours, as close as possible to 30 hours after swallowing the patency capsule unless they report to the study team that they visibly saw the excreted capsule. If the patency capsule has passed through the bowel then the subject will continue with WCE procedures.
 - *The study doctor or the subjects regular GI doctor or an appropriate delegate will discuss the results of MRE and patency capsule with the subject and guardian to decide if is a possible increased risk of retention and families will be able to decide if they would like to continue with study procedures. GI providers will be added to the MARS electronic IRB submission form and listed as study staff when they refer a subject so they are identified as being able to participate in these study procedures.*
- WCE Visit
 - The subject will return to the GI clinic to complete the WCE 5 days (\pm 2 days) from the time of patency capsule ingestion. Subject dietary restrictions the day before the wireless capsule endoscopy (WCE) visit.
 - To allow for greater flexibility for those subjects who are in school at the time of study procedures. The miralax prep may be started after school however the no solid foods after noon must still be observed.
 - Subject will fast for 8 hours overnight.
 - WCE visit (approximately 1 hour) - performed as a part of the research study.
 - The WCE used in this study is the PillCam SB video capsule (Given Imaging, Israel) that measures 11mm \times 26mm and weighs less than 4 g.
 - Subjects will wear a belt sensor around their waist and a recording device attached to it for the duration of the WCE study. device

- Subject will be asked questions about any symptoms and/or new medications.
- Subject will swallow the capsule in GI procedure room.
- Subjects should not be around electromagnetic fields while WCE procedure is performed

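### Section 4 recruits 50 and Section 8 recruits 40 with nothing to reconcile them; 40 recruits at about 20% screen failure give about 32 evaluable, not 34

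*Combined protocol and SAP*

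**What the plan says.** Section 4 (Target Study Population Specifics) opens with the target: "Study participants (n=50) ages 4 – 17.99 years of age will be recruited for this study".

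Section 8 (Statistical Considerations, sample size determination) asks for 34 participants for 80% power and then gives a different target: "We anticipate around 20% screen failure rate and intend to recruit 40 subjects to obtain a sample size of 34 evaluable subjects". It describes one kind of screen failure: "Subjects whose MRE results show findings that are contraindicated with WCE will be considered screen failures".

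Other sections describe further ways to leave before the capsule study:

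- Section 3 (Study Design), on the MRE result: "If MRE shows stenosis or stricture subject and caregivers will be given the opportunity to continue with the study or withdraw".
- Section 5 (Study Procedures), on the patency capsule: "If the patency capsule has passed through the bowel then the subject will continue with WCE procedures".
- Section 5, once the MRE and patency-capsule results have been discussed: "families will be able to decide if they would like to continue with study procedures".

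**The concern.** Sections 4 and 8 both speak of recruiting, so the wording does not support reading 50 as children approached and 40 as children enrolled. A team following Section 4 would stop at 50, and one following Section 8 at 40. The patency capsule and the wireless capsule endoscopy (WCE) are done only for research (Section 5), so the choice also decides how many children undergo them.

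Within Section 8, the recruitment number, the loss rate and the evaluable number should fit together, and they do not. The 34 comes from the power statement and the 20% is an assumption, so the 40 is the figure that fails to follow.

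The loss rate has no clear scope. Section 8 mentions only MRE findings, while Sections 3 and 5 add patency-capsule failure and family choice. Section 8 treats MRE contraindications as screen failures, whereas Section 3 lets a family continue after stenosis or stricture on MRE. The plan does not say whether such a child counts towards the 20%.

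**Working it through.** **Inputs**

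- Recruitment target: 50 (Section 4) and 40 (Section 8).
- Evaluable number: 34 (Section 8, taken as given).
- Screen failure: about 20% (Section 8). The range of 15% to 25% used below is an assumed reading of that approximate rate.

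**1. The two targets**

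50 − 40 = 10, and 10/40 = 25%.

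**2. Section 8's own figure**

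Recruits needed = evaluable / (1 − loss) = 34/0.80 = 42.5, so 43. The stated 40 is not reproduced.

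In the forward direction, 40 × (1 − 0.20) = 32, two short of 34.

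The loss rate at which 40 recruits yield 34 is 1 − 34/40 = 15.0%.

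A possible origin of the 40 is multiplying by 1 + loss instead of dividing by 1 − loss: 34 × 1.20 = 40.8. This is an inference; the plan does not show its calculation.

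**3. Whether 50 follows from Section 8**

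50 × 0.80 = 40 evaluable. Ending at 34 from 50 implies a loss of 1 − 34/50 = 32.0%, not about 20%. So 50 is not simply Section 8's calculation with its loss allowance added.

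**4. Evaluable children by target and loss rate (rounded down)**

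| Recruited | 15% loss | 20% loss | 25% loss | Largest loss that leaves 34 |
|---|---|---|---|---|
| 40 | 34 | 32 | 30 | 1 − 34/40 = 15.0% |
| 43 | 36 | 34 | 32 | 1 − 34/43 = 20.9% |
| 50 | 42 | 40 | 37 | 1 − 34/50 = 32.0% |

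Forty recruits reach 34 only at the favourable end of the assumed range.

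**5. Chance of reaching 34**

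If each child is independently evaluable with probability 0.80, the binomial probability of at least 34 evaluable is about 29% from 40 recruits, 65% from 43 and 99% from 50.

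**6. What cannot be computed**

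The document gives no patency-capsule failure rate, so that loss has no size here. Section 8 states a 23% difference but neither the two detection rates nor the discordance between the paired tests, so power at any of these evaluable numbers cannot be derived from the plan.

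**The case against.** The strongest reply is that the arithmetic gap is loose rounding. The rate is approximate, 40 recruits give exactly 34 at 15%, and two children hardly matter. Most of this stands. In every scenario tried with assumed detection rates or discordance, going from 34 to 32 cost about 2 to 3 percentage points of power. With McNemar's test and an assumed 24% of pairs discordant, for example, power fell from 81% to 79%. The gap is therefore a supporting point. It does not touch the conflict between 50 and 40, which no rounding explains.

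A second reply is that 50 is ample, so nobody is harmed. It is true that 50 tolerates a 32% total loss, and no underpowering is claimed. But the plan does not say that 50 governs, and the section carrying the power statement says 40.

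A third reply is that Sections 3 and 5 fit together as successive steps, and that Section 8 may mean MRE findings other than stenosis or stricture. That is possible: Section 2 names obstruction and fistulas among the likely contraindications to WCE. The tension between Sections 3 and 8 is thus not a proven contradiction, but the scope of the 20% is still undefined.

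Finally, incomplete capsule studies may be a further loss. Section 2 cites a paediatric series in which 22% of studies were incomplete, and the plan does not say whether an incomplete study is evaluable. Purely as an illustration, if it were not, and this rate came on top of 20% screen failure, 50 recruits would give 50 × 0.80 × 0.78 = 31.2 evaluable. This is a reason to define the loss rate with care and does not weaken the concern.

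**Conclusion.** The concern holds. The recruitment target differs by 10 children between two current sections, and nothing reconciles them. Section 8's target also does not follow from its own inputs: at 20% loss, 40 recruits give 32, and 34 needs 43. The first defect is the important one; the second is two children on an approximate rate.

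The consequence is an ambiguous sample size, not demonstrated underpowering. This conclusion takes 34 as given; the document does not supply what is needed to verify it. The table's range rests on reading the stated rate as 15% to 25%, and the probabilities rest on independent losses at exactly 20%. The conflict between the sections depends on none of these assumptions.

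**What to change.** State one recruitment number in Sections 4 and 8, derived as evaluable / (1 − loss), with the matching loss rate and evaluable number. Any of these would be consistent:

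- **Use 50.** It is already in Section 4 and gives 40 evaluable at 20% loss, or 34 with up to 32% total loss. Section 8 changes; up to 10 more children are recruited than it now plans.
- **Use 40.** Restate about 32 evaluable at 20% loss and recompute power. Section 4 changes, and the stated evaluable number becomes slightly less favourable.
- **Use 43.** This gives 34 evaluable at 20% total loss. Both sections change; three more children are recruited than Section 8 plans.

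Under each option:

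- State the two assumed detection rates or the discordance, so that the evaluable number can be checked. For 40 this must come first, because power has to be recomputed.
- Say that the loss rate covers every exit before a WCE result (MRE findings, patency-capsule result, family decision), and whether an incomplete capsule study counts as evaluable.
- Reconcile Sections 3, 5 and 8 on which exits are screen failures. Which children proceed to the capsule is a clinical matter for the investigators; the statistical need is only that the sections agree.

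The cost is wording in two sections, a sentence defining the loss rate and, if 40 is kept, one power calculation.
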